11.3. Analysis populations

The primary analysis population will include all eligible participants for whom data is available. Participants will be analysed according to their randomised group assignment irrespective of the intervention they actually received or adherence of intervention. Participants who withdraw from the trial will be included in the analysis until the point at which they withdrew. Data from participants who withdraw from the intervention and or active follow-up will continue to be included in the analysis as far as the data are available.

Other analysis populations for secondary analysis will detailed in the SAP.

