5.4. Potential Risks

During the trial, participants will continue to receive usual care regardless of randomisation group. As such we anticipate that the potential risks are low. Particular issues include a participant in the self-management group obtaining an excessively high or low BP reading and the possibility of increased anxiety due to the study. We aim to minimise any potential risks due to poor blood pressure control by ensuring women have clear advice regarding when to seek urgent medical help. The participant guideline/booklet will give clear advice to women to contact their healthcare professionals (e.g. obstetrician, midwife, general practitioner (GP) dependent on timing) in the case of maintained high or low readings. This will be reinforced by messages from the app when they submit a blood pressure reading that is outside the target range.

The first 14 days postpartum

Women in the self management group will also receive usual blood pressure monitoring and management by their community midwife and GP following their discharge from hospital. For women with high blood pressure, in the first 14 days after birth, NICE recommends that BP is monitored on at least alternate days (NICE, 2023). Therefore, in the first 2 weeks following discharge, reminders for self-monitoring are more frequent but usual care will continue fulfilling NICE requirements.

From 14 days postpartum

From 14 days after delivery until antihypertensive treatment is discontinued, women will be encouraged with reminders via the app to upload their readings. If a participant is unable to engage, it will be deemed that the woman has discontinued from the intervention but follow-up will continue unless the participant wishes to definitively withdraw.

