8. PARTICIPANT IDENTIFICATION

8.1. Study Participants

Women in the postnatal period with all types of pregnancy hypertension, requiring anti-hypertensive treatment. Information will be available at antenatal clinics. Identification will be antenatally or postnatally up to 7 days and randomisation within 7 days of child birth.

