8.2. Inclusion Criteria

- Participant is willing and able to give informed consent for participation in the study.
- People who have given birth within the last 7 days
- Aged 18 years or above.
- Participant with pregnancy hypertension including: chronic/essential hypertension (predating current pregnancy or requiring treatment before 20/40), or gestational hypertension (new-onset hypertension from 20/40 of index pregnancy) or pre-eclampsia (hypertension (GH or with proteinuria or metabolic changes), prior to their discharge from hospital post-delivery.
- Participant still requiring antihypertensive medication at randomisation following delivery.
- Able and willing to comply with trial requirements.
- Willing to allow their primary and secondary healthcare teams, if appropriate, to be notified of participation in the trial.
- Access to a smartphone compatible with the app.

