9.7. Randomisation

Participants will be randomised by the site study team after the baseline visit and before primary hospital discharge, using a secure web-based randomisation system provided by the Oxford Primary Care Clinical Trials Unit. If a participant has been discharged from hospital before being randomised the research midwife will contact the participant and carry out remote consent and randomisation over the phone within 7 days of being discharged. The system will allow for the allocation of participants to the two

randomisation groups: usual care or self-management on a 1:1 basis and for this allocation to be stratified according to recruitment site with minimisation for principal diagnosis (chronic hypertension or gestational hypertension/pre-eclampsia), and mean postnatal diastolic blood pressure (last 3 readings in clinical record, <83mmHg vs \geq 83mmHg), and number of antihypertensive medications (<2 vs \geq 2 medications).

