9.10. Early Discontinuation/Withdrawal of Participants

During the course of the study a participant may choose to discontinue early from the study intervention at any time. This may happen for several reasons, including but not limited to:

- The occurrence of what the participant perceives as an intolerable AE related to the intervention.
- Inability to comply with study procedures
- Participant decision

Participants may choose to stop intervention and/or study assessments including urinary sample provision, but may remain on study follow-up.

Participants may also withdraw their consent to withdraw from the study completely. In the case of withdrawal from both treatment and active follow up, a participant's data and samples obtained up until the point of withdrawal will be retained for use in the study analysis. No further data or samples would be collected after withdrawal.

In addition, the Investigator may discontinue a participant from the study treatment at any time if the Investigator considers it necessary for any reason including, but not limited to:

- Ineligibility (either arising during the study or retrospectively having been overlooked at screening)
- Significant protocol deviation
- Clinical decision
- Loss of capacity to consent to involvement in research, for example due to developing puerperal psychosis
- Loss to follow up

Non adherence in either group would be defined as missing a trial visit, and not being contactable to reschedule the visit. Non adherence in the intervention arm is defined as failing to report 3 consecutive blood pressure readings in the first 14 days after birth, or 5 consecutive blood pressure readings from this point onwards. The definition of "significant non adherence necessitating discontinuation from the study" will be an individualised judgement made by the research team in conjunction with a participant's direct care team. This judgement will be made on the basis of concerns regarding participant safety, and therefore will be influenced by the nature, frequency and clinical impact of a particular participant's non-adherence.

If a participant from the intervention arm discontinues from the study, they will continue usual postnatal care including blood pressure monitoring with their community midwife and GP.

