11.1.1 Description of the Statistical Methods

All analyses will be conducted in accordance with Oxford Primary Care CTU SOPs.

Internal pilot: Descriptive statistics will be used to describe recruitment of the first 100 participants (section 9.12).

In accordance with CONSORT guidelines, we will record and report participant flow. Descriptive statistics of recruitment, drop-out/withdrawal and completeness of intervention will be reported.

Baseline variables will be presented by randomised group using frequencies (with percentages) for binary and categorical variables and means (standard deviations) or medians (with lower and upper quartiles) for continuous variables. There will be no tests of statistical significance nor confidence intervals for differences between groups on any baseline variables.

The primary estimand is the mean difference in daytime ambulatory diastolic BP at 22-39 weeks for all randomised participants, as defined by protocol eligibility criteria, regardless of what intervention they actually received or adherence of intervention. A generalised linear mixed-effects model utilising data collected all time-points from randomisation will be fitted to the data with mean daytime diastolic BP measured at 22-39 weeks as the response variable, adjusting for minimisation factors for principal diagnosis (chronic hypertension or gestational hypertension/pre-eclampsia), mean postnatal diastolic blood pressure (last 3 readings in clinical record) ($<83/\ge83$), number of anti-hypertensive medications ($<2/\ge2$) and randomised group fitted as fixed effects and the model will include site as a random effect. An adjusted mean difference at 22-39 weeks between the randomised groups, together with a 95% confidence interval and a P value, will be estimated from the model.

A similar approach will be used for continuous secondary outcomes, and generalised linear model for binary outcomes. Time effects will be included in the model for repeated measures outcomes where appropriate.

Safety outcomes will be compared using Fisher's exact or Chi-square test.

Pre-specified subgroup analyses of the primary outcome will be explored by baseline diastolic BP, principal diagnosis, ethnicity, indices of multiple deprivation quintiles, social status, and parity.

Standard residual diagnostics will be assessed for the appropriateness of the model.

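### The primary analysis is limited to eligible women with data, while conflicting rules on the randomisation window and on discontinuation leave unclear which randomised women it keeps

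*Protocol*

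**What the plan says.** **Population.** Protocol section 11.3 fixes the primary population: "The primary analysis population will include all eligible participants for whom data is available". It goes on to analyse women in their assigned arm whatever they received or adhered to, and to keep such data as exist from women who withdraw. Only the other populations, for secondary analyses, are left to the SAP. Section 11.1.1 places the primary estimand in a slightly different group: "for all randomised participants, as defined by protocol eligibility criteria, regardless of what intervention they actually received or adherence of intervention". Section 9.10 lists ineligibility, whether it arises during the study or is noticed later, among the reasons an investigator may stop study treatment. Under section 9.5, participants, recruiting clinicians and the trials unit's data managers know the allocation; the analyst is blinded.

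**Randomisation window.** Section 8.1 specifies "randomisation within 7 days of child birth" and the inclusion criterion in section 8.2 reads "People who have given birth within the last 7 days". Sections 9.1.1 and 9.4 also tie the baseline visit to 7 days from delivery. For a woman already at home, section 9.7 has the research midwife "carry out remote consent and randomisation over the phone within 7 days of being discharged".

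**Discontinuation.** For a woman who cannot engage with the app after day 14, section 5.4 says "it will be deemed that the woman has discontinued from the intervention but follow-up will continue", unless she wants to withdraw altogether. Section 9.10 provides for "significant non adherence necessitating discontinuation from the study", decided case by case by the research team with the care team on safety grounds. It defines non-adherence in two ways: for either arm, a missed visit with no contact to rebook; for the intervention arm only, 3 consecutive unreported readings in the first 14 days after birth, or 5 thereafter.

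**The concern.** An as-randomised comparison is protected by keeping every randomised woman in it. Restricting the population by the word *eligible* reopens membership after allocation, and the protocol does not say who judges eligibility for the analysis, when, or whether blind to arm. Site staff and data managers know the arm, so a judgement made late is open to influence. The word would matter little if ineligible randomised women could hardly occur, but two sections of the protocol disagree on who may be randomised.

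The discontinuation wording raises a separate problem. If leaving the study ends follow-up before 22-39 weeks, there is no ambulatory reading, and the woman is lost through the requirement that data be available. One of the two non-adherence definitions exists in the self-management arm only, so such losses could be uneven. Section 11.2 already reports ambulatory completion below 50%, so avoidable further loss of the primary outcome deserves attention.

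**Working it through.** **1. The two population statements.** Section 11.1.1 names all randomised participants, qualified by the protocol eligibility criteria. Section 11.3 names eligible participants with data. The qualifier in 11.1.1 has two readings: a description of whom the trial enrols, or a filter on the women randomised. Under the first, 11.3 is narrower than the estimand. Under the second, the sections agree, but neither covers every randomised woman. Either way, the status of a randomised woman later found ineligible is not settled.

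**2. Whether the protocol can create such women.** Count days from birth, with discharge on day *x*.
- Latest randomisation under 9.7: day *x* + 7.
- Latest randomisation under 8.1 and 8.2: day 7.
- The rules differ for every *x* above 0.
- Example: discharge on day 4, randomisation on day 10. Time from discharge is 10 − 4 = 6 days, within 7. Time from birth is 10 days, beyond 7. She satisfies 9.7 and fails 8.2.

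The interval from birth to randomisation is fixed before the arm is known, so this conflict is the same in both arms. It biases the comparison only if the decision to keep or drop such women is made with knowledge of arm or outcome.

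**3. Discontinuation.** Section 5.4: the intervention stops and follow-up continues. Section 9.10: discontinuation from the study is possible. Section 11.3 does not exclude non-adherent women. They can be lost only indirectly: discontinued from the study, then no 22-39 week ambulatory measurement, then no primary outcome.

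**4. The sample size is not in dispute.** Inputs from section 11.2: difference 4 mmHg, SD 10 mmHg, alpha 0.05 (two-sided by section 11.6), power 90%, dropout 15%.
- Normal approximation: 2 × (1.960 + 1.282)² × (10/4)² = 131.3, so 132 per arm. The t-test solution is 132.3, so 133 per arm, 266 in total.
- 133 / 0.85 = 156.5, so 157 per arm and 314 in total, as stated.
- 266 / 0.5 = 532, as stated.

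Defining the population as all randomised women changes none of these.

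**5. What selective loss could do (illustration only).** If a share *f* of one arm is removed and its mean diastolic pressure differs by *d* from the women kept, the between-arm difference shifts by *f* × *d*. The protocol gives neither value. Assumed ranges: *f* from 2% to 15%, *d* from 2.5 to 10 mmHg.

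| *f* | *d* (mmHg) | Shift (mmHg) | Share of 4 mmHg |
|---|---|---|---|
| 2% | 2.5 | 0.05 | 1.25% |
| 5% | 5 | 0.25 | 6.25% |
| 10% | 5 | 0.50 | 12.5% |
| 15% | 10 | 1.50 | 37.5% |

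The sign follows the sign of *d* and the arm affected. If both arms lose the same share with the same *d*, the shift is *fd* − *fd* = 0. With 133 per arm, power is 90.1%; removing 5% or 15% of one arm gives 89.4% or 87.6%. The question is one of bias, not power.

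**The case against.** The strongest reply is that nothing in the protocol says a woman later found ineligible is removed from the dataset. Section 9.10 speaks of stopping her study treatment and, for women who withdraw fully, of keeping data already collected. Section 11.3 analyses as randomised irrespective of adherence, and section 9.5 blinds the analyst. All of this is correct. It means exclusion is permitted by the wording, not prescribed. It does not say what *eligible* does in the definition, and that definition is fixed here, not deferred to the SAP.

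On the window, four sections count from delivery or birth and 9.7 is the outlier; the conflict is symmetric between arms. That stands, and it limits the point to unclear membership.

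On discontinuation, a reader might infer that the plan removes poorly adherent self-management women and so favours the intervention. The documents do not support this. Missed readings do not trigger removal automatically; the decision is individual and safety-based. The missed-visit definition covers both arms. Sections 5.4 and 9.10 overlap but need not clash in every case. Missing outcomes are addressed in section 11.7 by a mixed model assuming data missing at random, multiple imputation and a pattern-mixture analysis. What remains is that the two sections give different answers on whether follow-up continues, and that planned handling of missing data does not replace collecting an obtainable outcome.

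**Conclusion.** The point holds as a defect in wording that should be corrected. The primary population and the estimand both carry an undefined eligibility condition, the protocol can produce randomised women whose eligibility depends on which section is read, and it is unclear whether women discontinued for non-adherence still have their primary outcome collected.

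No size or direction of bias follows from the documents. The shifts of 0.05 to 1.5 mmHg above span a thirtyfold range and reflect only the assumed inputs, including the assumption that loss falls on one arm. A claim that the comparison is biased, or biased towards self-management, would need evidence that eligibility was judged with knowledge of arm or outcome, or that outcome loss differed by arm and was related to blood pressure. The protocol supplies neither.

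**What to change.** 1. In sections 11.1.1 and 11.3, define the primary population as all randomised women in the arm assigned, including any later found ineligible. Remove or explain the eligibility qualifier in 11.1.1; changing 11.3 alone would leave the ambiguity in the estimand.
2. Reconcile section 9.7 with sections 8.1, 8.2, 9.1.1 and 9.4 so that the window has one anchor. Keep women already randomised under either reading in the analysis.
3. Reconcile sections 5.4 and 9.10. State separately whether outcome collection, including the ambulatory measurement, continues after a woman is discontinued for non-adherence. The clinical rule for stopping is for the investigators to settle.

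The cost is wording, and a few women outside the strict criteria stay in the analysis. The sample size does not change.

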11.4. Decision points

There will be no planned interim analysis for efficacy and futility. Data on trial progress such as recruitment and participant drop-out of the trial and quality of data will be reported to both TSC and DMC as specified in the charters. Only the trial statistician and DMC will have access to unblinded results with blinded group allocation maintained throughout the trial until the analysis is complete.

The traffic light approach will be used for assessment of the internal pilot after recruitment of the first 100 women within six months to assess viability of the trial (section 9.12). Decisions regarding the success or otherwise of the internal pilot will be overseen by the TSC and DMC at around 7 months after the first participant has been randomised, to give time for data lock after 6 months.

11.5. Stopping rules

There are no predetermined stopping rules. Any consideration of the need for termination of the trial will be on the advice of the DMC to TSC who will make the decision whether or not to terminate the trial.

11.6. The Level of Statistical Significance

The level of significance will be set at 5% two-sided significance level. P-values will be adjusted for any multiple comparisons in order to maintain an overall type I error rate of 5%.

11.7. Procedure for Accounting for Missing, Unused, and Spurious Data.

Missing data in all outcomes will be inspected and reported, with reasons given where available and missing data mechanism explored across randomised groups. We will explore the mechanism of missing data, though the mixed effects model implicitly accounts for data missing at random. Factors found to be predictive of missingness will be included as fixed effects in the analysis models.

Additional sensitivity analysis using imputation methods, such as multiple imputation for data missing will be performed and a pattern mixture model for longitudinal data will be fitted to assess the robustness of the missing at random assumption required for mixed effect models.

11.8. Procedures for Reporting any Deviation(s) from the Original Statistical Plan

The final statistical analysis plan will be agreed prior to final data lock and prior to any analyses taking place. Any deviation thereafter will be reported in the final trial report.

11.9. Health Economics Analysis

11.9.1 Health Economic Analysis Plan (HEAP)

The health economic aspects of the study are summarised here. A detailed health economic analysis plan will be developed prior to data lock.

11.9.2 Within-trial economic evaluation

An economic evaluation using an NHS perspective will be conducted as an integral part of the SNAP2 trial. This analysis will take the form of a cost-consequences analysis and will utilise participant-level data collected during the trial to determine whether there are differences in costs and participant health outcomes between treatment arms over the first 12-months of intervention implementation.

We will collect health care resource use and health-related quality of life data using participant questionnaires at baseline, 12, 22-39 and 48-60 weeks follow-up. In terms of resource utilisation, we will capture details of antihypertensive medications prescribed, hospital inpatient admission and outpatient visits, and primary care contacts. Unit costs to value these healthcare contacts will be obtained from established national sources, including the National Schedule of NHS Costs and the Personal and Social Services Research Unit (Curtis, 2020). A bottom-up costing approach will be employed to estimate the healthcare costs associated with self-management (e.g. the home blood pressure monitor, participant training in the use of the monitor and app, and physician time spent reviewing and approving medication

changes). Participant health-related quality of life will be assessed at trial entry and each follow-up using the EuroQol EQ-5D-5L instrument (Herdman, 2011). Value sets to derive utility scores for EQ-5D-5L states are currently under development for a UK setting but should be finalised by the time of the analysis.

Mean (standard deviation) estimates of resource use, costs and quality of life will be reported separately for each trial arm. When comparing between trial arms, mean differences (95% confidence intervals) calculated using regression methods adjusted for key baseline characteristics, will be used. We will use multiple imputation to deal with missing data and will present within-trial results for key sub-groups as specified by trial's clinical team.

11.9.3 Model of longer-term costs and effects of BP self-management and usual care versus usual care alone

Better blood pressure control post-pregnancy offers the potential for lower blood pressure and a reduced risk of cardiovascular disease and stroke over the longer-term. We will therefore utilise health economic modelling to extrapolate the longer-term costs and consequences of any reduction in post-pregnancy blood pressure observed with self-management during the trial. We will adapt a decision analytic Markov model we previously developed to simulate the long term costs and outcomes of blood pressure self-monitoring during pregnancy, and from an NHS perspective, will simulate lifetime healthcare costs and quality-adjusted life years (QALYs) of blood pressure self-management versus usual care alone.

The model will comprise a number of mutually exclusive health states including an 'alive and well' state and various cardiovascular event states. The cohort entering the model will be matched in characteristics (e.g. age, ethnicity, BMI, type of hypertension, blood pressure etc.) to participants in the SNAP2 trial and published data will be used to estimate how the cohort transitions between the health states on an annual basis. Annual risks of a first cardiovascular event for example will be estimated by entering cohort characteristics into established prediction tools such as Framingham and Q-Risk, and then further augmenting these predictions for the additional risks associated with pregnancy hypertension and its adverse events. The treatment effect, modelled as a reduction in predicted cardiovascular risk attributable to a lowering of diastolic blood pressure, will be informed by the trial data. The health-related quality of life and cost implications of the various cardiovascular disease events will be sourced from the published literature and included within the model.

Running the model will generate predicted lifetime mean healthcare costs and QALYs with self-management and with usual care. A comparison between model arms will be made and results expressed using an incremental cost per QALY gained. This figure will be compared to current thresholds for value for money (NICE, 2008). Uncertainty surrounding the model's input parameters and results will be handled using probabilistic sensitivity analysis and presented using cost-effectiveness acceptability curves. Sensitivity analysis will explore the implications of varying the analysis time horizon upon uncertainty and the cost-effectiveness results. The model will be constructed such that the characteristics of the cohort entering the model can be altered and cost-effectiveness explored for subgroups differentiated for example by ethnicity or social deprivation.

All analyses will be conducted in line with current good practice guidance on undertaking and reporting the findings of economic evaluations and decision analytic models (Caro, 2012).

